10.4.3 Secondary Efficacy Endpoint(s)

The analyses and summary statistics for all secondary efficacy endpoints, as specified in Table 4-1, will be presented in appropriate tables. The 90% confidence intervals and p values will be provided, as needed, by applying appropriate statistical models to each endpoint that will be specified in detail in the SAP.

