4 OBJECTIVES AND ENDPOINTS

Table 4-1: Objectives and Endpoints

Objectives	Endpoints
Primary	
Efficacy	
To evaluate the efficacy of deucravacitinib versus placebo at Week 24	Change from baseline in SALT score at Week 24
Safety	
To evaluate the safety and tolerability of deucravacitinib versus placebo	 Incidence of SAEs, AEs, AEs leading to study discontinuation, and AEIs Change in laboratory, ECG, physical examination, and vital sign parameters over time
Secondary	
Efficacy	
To evaluate the efficacy of deucravacitinib versus placebo on additional endpoints at Week 24	 Proportion of participants achieving a ≥ 50% reduction in SALT score (SALT50 response) from baseline at Week 24 Proportion of participants achieving a SALT score ≤ 20 at Week 24 Proportion of participants achieving an AA-IGA score of 0 or 1 at Week 24 with at least a 2-point change from baseline

Protocol Amendment No.: 02

Table 4-1: Objectives and Endpoints

Approved v 3.0 930159159 3.0

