6.1 Inclusion Criteria

- 1) Signed Written Informed Consent
 - a) Participant must be willing and able to participate in the study and sign the ICF
 - b) Participant must be willing and able to complete all study-specific procedures and visits

2) Type of Participant and Target Disease Characteristics

- a) Documented clinical diagnosis of AA for at least 6 months
- b) Current episode of scalp hair loss (at Screening) must meet the following criteria:
 - i) Duration at least 6 months
 - ii) Duration of current hair loss episode of AA affecting ≥ 50% of the scalp not exceeding 8 years
 - iii) Scalp hair loss has been stable (ie, no significant spontaneous regrowth [> 10%] over the last 6 months)
- c) SALT score ≥ 50 at Screening and Day 1 (see Appendix 5)
 Participant with complete scalp hair loss (SALT score of 100) with or without body hair involvement can be included.
- d) Participant must have an Alopecia Areata Investigator Global Assessment (AA-IGA) grade ≥ 3 at Screening and Day 1.
- e) Participant should not shave their scalp from 7 days prior to the Screening visit and agree to not shave their scalp 7 days prior to each study visit, to allow for SALT assessment of hair regrowth. If participant is using a hairpiece or wig, the participant must be willing and able to remove the hair prosthetic at each appointment. Participant should maintain a stable hair style to allow for reliable and consistent assessment of SALT throughout the study.
- f) Participant with current or a history of androgenetic alopecia can be included as long as, in the opinion of the investigator, the participant has either of the following classifications: Ludwig Scale³⁰ ≤ II for women; Hamilton-Norwood Scale³¹ ≤ III for men.

Protocol Amendment No.: 02

Note: A male participant with Hamilton-Norwood III vertex or Hamilton-Norwood IIIa classification will be excluded.

3) Age of Participant

a) Men and women aged ≥ 18 years to ≤ 65 years at the time of Screening visit.

4) Reproductive Status

- Investigators shall counsel women of childbearing potential (WOCBP) participants, and male participants who are sexually active with WOCBP, on the importance of pregnancy prevention and the implications of an unexpected pregnancy.
- The investigator shall evaluate the effectiveness of the contraceptive method in relationship to the first dose of study intervention.
- Local laws and regulations may require the use of alternative and/or additional contraception methods.

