9.1 Efficacy Assessments

The efficacy assessments listed below are commonly used tools to characterize disease severity in patients with AA and are established endpoints in clinical practice for assessing treatment efficacy in AA

All investigator-administered assessments should be performed by a dermatologist or appropriately trained licensed health care provider who is experienced in the assessment of patients with AA. All efficacy evaluators must receive and document protocol-specific efficacy assessment training prior to performing the evaluations.

To ensure consistency and reduce variability, the same evaluator must assess all dermatological clinical evaluations for any individual participant throughout the study whenever possible; a back-up experienced, qualified, and protocol-trained evaluator will only be allowed on rare occurrences, when the designated evaluator is unable to perform the evaluation.

[figure not shown]
• SALT Assessment (Appendix 5^{32,33}) This is a quantitative rating scale for measuring the severity of terminal hair loss in each of the 4 quadrants of the scalp: posterior (back), vertex (top), left, and right profile. To obtain a SALT score, the degree of scalp hair loss is assessed as a percentage of each scalp region affected and is multiplied by its respective weighting factor (the scalp surface area) for each of the 4 sections in order to provide a subtotal for each region. The SALT score is the sum of these subtotals. SALT scores can range from 0 (no hair loss) to 100 (total scalp hair loss).

SALT50 indicates at least a 50% improvement from baseline in the SALT score at a particular time point, indicating 50% hair regrowth.

The proportion of participants achieving these responses will be assessed at all visits.

• AA-IGA: The AA-IGA utilizes a 5-point scale, in which the investigator assesses scalp hair loss based on the SALT assessment. The AA-IGA measures AA severity at a single point in time (without taking into account the baseline disease condition). The participant's scalp hair loss, as it looks at the time of evaluation, is scored as none (0) (0% scalp hair loss), limited (1) (1%-20% scalp hair loss), moderate (2) (21%-49% scalp hair loss), severe (3) (50%-94% scalp hair loss), or very severe (4) (95%-100% scalp hair loss).

Protocol Amendment No.: 02 Date: 29-Aug-2023

Protocol Amendment No.: 02 Date: 29-Aug-2023

te: 29-Aug-2023

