10 STATISTICAL CONSIDERATIONS

10.1 Statistical Hypothesis

Let μ_1 and μ_2 be the population means of change from baseline at Week 24 in SALT for 6 mg QD and 6 mg BID dosages of deucravacitinib, respectively, and μ_0 be the population mean of change from baseline at Week 24 in SALT for placebo; the 2 primary hypotheses for this study are:

- 1) $H0_1$: $\mu_1 = \mu_0$ versus $H1_1$: $\mu_1 \neq \mu_0$
- 2) $H0_2$: $\mu_2 = \mu_0$ versus $H1_2$: $\mu_2 \neq \mu_0$

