10.4.2 Primary Efficacy Endpoints

The 2 primary hypotheses, as specified in Section 10.1, will be tested on the overall significance level of 10%. To strongly control the overall type I error at 10% level, the Bonferroni adjustment will be used to adjust multiplicity due to 2 deucravacitinib dose arms to be compared with the placebo arm.

The primary efficacy endpoint (change in SALT score from baseline to Week 24 [Day 169]) will be analyzed on the randomized population using an analysis of covariance (ANCOVA). The ANCOVA model will include treatment arm, the randomization stratification variable of alopecia episode duration (< 4 years and ≥ 4 years), as factors, and baseline SALT score as a covariate.

The primary methodology to impute the missing data will be multiple imputation with the assumption of missing at random.

Additional sensitivity analyses will be further outlined in the SAP.

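### Do 90% intervals on the secondary endpoints, two of which nearly coincide, overstate the secondary evidence?

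*Combined protocol and SAP*

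**What the plan says.** Section 10.1 sets out two-sided hypotheses for the Week 24 change in SALT, one per dose against placebo. Section 10.4.2 then says of these two hypotheses: "To strongly control the overall type I error at 10% level, the Bonferroni adjustment will be used to adjust multiplicity". The share per dose, 0.10/2 = 0.05, is not printed there but follows directly.

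Section 10.4.3 covers the secondary endpoints: "The 90% confidence intervals and p values will be provided, as needed, by applying appropriate statistical models to each endpoint". It leaves the models to the SAP. It names no alpha, testing order or dose adjustment, and it does not say whether the results are confirmatory or descriptive.

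Table 4-1 in Section 4 lists three secondary efficacy endpoints at Week 24: SALT50, SALT ≤ 20, and "Proportion of participants achieving an AA-IGA score of 0 or 1 at Week 24 with at least a 2-point change from baseline". Section 9.1 describes AA-IGA as a scale "in which the investigator assesses scalp hair loss based on the SALT assessment", with grade 0 for no loss and the next grade "limited (1) (1%-20% scalp hair loss"). Section 6.1 requires a baseline SALT of at least 50 and also states: "Participant must have an Alopecia Areata Investigator Global Assessment (AA-IGA) grade ≥ 3 at Screening and Day 1".

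**The concern.** Two things stand out.

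- **Interval level.** A 90% interval matches the whole 10%, not the 5% that each dose receives in the primary analysis. A dose with a p value between 0.05 and 0.10 would fail on the primary endpoint, yet its secondary interval would exclude no effect.
- **Overlap.** AA-IGA 0/1 means at most 20% scalp hair loss, which is what SALT ≤ 20 measures. With a baseline grade of 3 or 4, any move to grade 0 or 1 is automatically at least two points, so the extra condition does nothing for an eligible participant.

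Together these could let a report count one result as two supporting findings, each judged more leniently than the primary. That would matter because Section 3.1 says the study should help identify the dosage with the best benefit/risk, and Section 10.4.1 says the Week 24 results will feed into later development.

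**Working it through.** **1. Confirm the per-dose level from the plan's own power.** Inputs from Section 10.2: difference 39, SD 43, 25 evaluable per arm (30 less 15% dropout, rounded down from 25.5). The noncentrality is 39 / (43 × √(2/25)) = 39 / 12.16 = 3.21 on 48 degrees of freedom.

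| Two-sided alpha | Plan | Noncentral t | Normal approximation |
|---|---|---|---|
| 0.10 | 93% | 93.5% | 94.1% |
| 0.05 | 88% | 88.1% | 89.4% |

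The plan's figures reproduce. The 88% row, which the plan labels as Bonferroni-adjusted, confirms 5% two-sided per dose for the primary.

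**2. Error over two doses, for one secondary endpoint.** With equal arms and a shared placebo group, each contrast has variance 2σ²/n and the two share a covariance of σ²/n, so their correlation is 0.5. Suppose neither dose works and any interval excluding no effect is called positive. The chance of at least one positive is then 1 − P(|Z₁| < c, |Z₂| < c):

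| Interval | c | Correlation 0.5 | Independent | Bonferroni bound |
|---|---|---|---|---|
| 90% | 1.645 | 17.5% | 19.0% | 20% |
| 95% | 1.960 | 9.1% | 9.75% | 10% |

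A 95% interval is wider by 1.960/1.645 = 1.19, or 19%.

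**3. Error over two doses and two distinct endpoints.** The documents give no correlation between SALT50 and SALT ≤ 20, so it is an assumption, varied here from 0.9 down to 0. The chance of at least one positive runs from 23% to 32% with 90% intervals and from 13% to 17% with 95% intervals. The wider intervals restore the dose split within an endpoint but still exceed 10% across endpoints.

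**4. Does the level change a reading?** It can at the margin. With assumed counts of 30 per arm and Newcombe intervals for the risk difference:

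| Active vs placebo | 90% lower limit | 95% lower limit |
|---|---|---|
| 4/30 vs 0/30 | +0.024 | −0.006 |
| 7/30 vs 2/30 | +0.012 | −0.020 |

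**5. How far do the endpoints overlap?** Take every whole-number pair of baseline SALT (50 to 100, 51 values) and Week 24 SALT (0 to 100, 101 values), which gives 51 × 101 = 5,151 pairs, and grade AA-IGA from the Section 9.1 cut points. SALT ≤ 20 and AA-IGA 0/1 with a two-point change disagree in none of them. SALT ≤ 20 also always implies SALT50, because the smallest possible reduction is 1 − 20/50 = 60%. The three endpoints thus carry two distinct outcomes, one nested in the other.

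In real data the match can break in three ways: a fractional SALT between 20 and 21 has no printed grade, the investigator records AA-IGA as a separate assessment, and a participant may be randomized in breach of the entry criteria.

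**The case for a change.** The best argument for acting is that the 90% level is already fixed in the protocol, while the status of the secondary results is left unsaid. Secondary results will inform dose choice. The Introduction also notes that SALT ≤ 20 was the primary endpoint in Phase 3 trials of another agent, so readers will give it weight. With 30 per arm, step 4 shows that the level can decide whether an interval touches zero. The remedy would be wording alone, and nothing in Table 4-1 or Section 9.1 warns the reader that two endpoints coincide.

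The facts in that argument stand; the need for a change does not follow from them.

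- The Bonferroni rule covers "the 2 primary hypotheses for this study are" and nothing else, so Section 10.4.3 departs from no rule. That the secondary results are unadjusted is read from silence, and the SAP detail is not in the text at hand.
- A 90% interval for one comparison covers at 90%. It is too narrow only for a simultaneous claim, and the protocol makes none.
- The p values are to accompany the intervals as needed. A reader who prefers 5% per dose can apply it directly, and changing the interval level would not move a single p value.
- Two outcomes that nearly coincide add almost nothing to type I error. The risk is double counting in the text of a report, not in the analysis.
- The two-point condition is a harmless safeguard. Efficacy is analysed on all randomized participants, so someone entered in error at grade 2 who reached grade 1 would not count as a responder.
- Demoting AA-IGA because it overlaps would not be consistent while SALT50 and SALT ≤ 20, which are nested, both stay.

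**Conclusion.** No change to the plan follows. The 90% level mirrors the study's overall 10% alpha. In a Phase 2 trial that Section 5.4 presents as a first look at efficacy and safety, the choice between 90% and 95% for secondary intervals is one on which statisticians reasonably differ. The difference is 17.5% against 9.1% per endpoint over two doses. It arises only if neither dose works and exclusion of no effect is taken as a finding, a rule that the protocol does not contain. Moving to 95% would widen the intervals by 19%, leave the p values alone, and still leave 13% to 17% across the two distinct endpoints under the assumed correlations.

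The overlap of AA-IGA 0/1 with SALT ≤ 20 is real for eligible participants, but removing the endpoint or its two-point condition would change essentially no result. What remains is a gap that analysts normally fill when reporting: describe the secondary intervals and p values as nominal, and say that the three endpoints are not independent evidence. This conclusion rests on the protocol text and would need another look if the SAP attached a formal success claim to any secondary endpoint.

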10.4.5 Other Safety Analyses

All safety analyses will be carried out on the safety population.

Adverse events will be monitored during the trial and the data analyzed with respect to incidence within each treatment arm as well as severity and potential relationship of the AEs to study intervention. Adverse events will be summarized for the safety population by System Organ Class

Protocol Amendment No.: 02

Date: 29-Aug-2023 65

and Preferred Term and presented in descending order of frequency within each System Organ Class. Serious AEs and AEs leading to discontinuation will be summarized similarly.

Associated laboratory parameters such as hepatic profile, renal function, and hematology values will be grouped and presented together. Changes from baseline to each visit for each laboratory parameter will also be summarized.

The change from baseline to each visit for each of the vital sign variables will be summarized. Abnormal vital sign values will be flagged and listed.

The change from baseline to each visit for each of the ECG parameters will be summarized.

10.4.6 Other Analyses

Not applicable.

10.5 Interim Analysis

Not applicable.

12 APPENDICES

Protocol Amendment No.: 02 Date: 29-Aug-2023

te: 29-Aug-2023

APPENDIX 1 ABBREVIATIONS

Term	Definition
AA	alopecia areata
AA-IGA	Alopecia Areata Investigator Global Assessment
AE	adverse event
AEI	adverse event of interest
ALT	alanine aminotransferase
ANCOVA	analysis of covariance
APTT	activated partial thromboplastin time
AT	aminotransaminase
AST	aspartate aminotransferase
AxMP	auxiliary medicinal product
BID	twice daily
BMS	Bristol-Myers Squibb Company
BP	blood pressure
BUN	blood urea nitrogen
Cavg	average concentration
CBC	complete blood count
CD	cluster of differentiation
CFR	Code of Federal Regulations
CI	confidence interval
CK	creatine kinase
Cmin	minimum observed concentration
COVID-19	coronavirus disease 2019
CRF	Case Report Form, paper or electronic
CRO	Contract Research Organization
CXCL	CXC motif chemokine ligand
D	Day
d	days
DDI	drug-drug interaction
DILI	drug-induced liver injury

Protocol Amendment No.: 02 Date: 29-Aug-2023

te: 29-Aug-2023

Term	Definition		
DMC	Data Monitoring Committee		
DNA	deoxyribonucleic acid		
ECG	electrocardiogram		
eCRF	electronic Case Report Form		
ED	early discontinuation		
eGFR	estimated glomerular filtration rate		
E-R	exposure-response		
FAS	Full Analysis Set		
FDA	Food and Drug Administration		
FIH	first-in-human		
FSH	follicle stimulating hormone		
GI	gastrointestinal		
HbA1c	hemoglobin A1c		
HBcAb	hepatitis B core antibody		
HBsAb	hepatitis B surface antibody		
HBsAg	hepatitis B surface antigen		
HBV	hepatitis B virus		
HCG	human chorionic gonadotropin		
Hct	hematocrit		
HCV	hepatitis C virus		
HDL	high density lipoprotein		
HF	hair follicle		
Hgb	hemoglobin		
HIV	human immunodeficiency virus		
hr	hour		
hs-CRP	high-sensitivity C-reactive protein		
IB	Investigator Brochure		
ICF	informed consent form		
IFN	interferon		

Term	Definition	
Ig	immunoglobulin	
IGRA	IFN gamma release assay	
IL	interleukin	
IMP	Investigational Medicinal Product	
INR	international normalized ratio	
IP	investigational product	
IRB	Institutional Review Board	
IRT	Interactive Response Technology	
IU	international unit	
IV	intravenous	
JAK	Janus kinase	
LDH	lactate dehydrogenase	
LDL	low density lipoprotein	
LTBI	latent TB infection	
MACE	major adverse cardiovascular events	
МНС	major histocompatibility complex	
min	minute	
N/A	not applicable	
NA	nucleoside/nucleotide analogues	
NK	natural killer	
NKG2D+	natural killer group 2D+	
PA	posteroanterior	
PASI	psoriasis area severity index	
PD	pharmacodynamics	
PE	physical examination	
PK	pharmacokinetics	
PO	per os	

Approved v 3.0 930159159 3.0

Term	Definition	
PsA	psoriatic arthritis	
PsO	plaque psoriasis	
PT	prothrombin time	
PTT	partial thromboplastin time	
QD	once daily	
RNA	ribonucleic acid	
SAE	serious adverse event	
SALT	Severity of Alopecia Tool	
SAP	statistical analysis plan	
SARS-CoV-2	severe acute respiratory syndrome coronavirus 2	
SD	standard deviation	
SLE	systemic lupus erythematosus	
SOA	Schedule of Activities	
STAT	signal transducer and activator of transcription	
Т3	triiodothyronine	
T4	thyroxine	
TB	tuberculosis	
TE	target engagement	
TSH	thyroid-stimulating hormone	
TYK2	tyrosine kinase 2	
UC	ulcerative colitis	
ULN	upper limit of normal	
WOCBP	women of childbearing potential	

APPENDIX 2 STUDY GOVERNANCE CONSIDERATIONS

The terms "participant" and "subject" refer to a person who has consented to participate in the clinical research study. Typically, the term "participant" is used in the protocol and the term "subject" is used in the Case Report Form (CRF).

REGULATORY AND ETHICAL CONSIDERATIONS

This study will be conducted in accordance with:

- Consensus ethical principles derived from international guidelines, including the Declaration of Helsinki and Council for International Organizations of Medical Sciences (CIOMS) International Ethical Guidelines
- Applicable International Council for Harmonisation (ICH) Good Clinical Practice (GCP) Guidelines
- Applicable laws, regulations, and requirements

The study will be conducted in compliance with the protocol. The protocol, any revisions/amendments, and the participant informed consent form (ICF) will receive approval/favorable opinion by Institutional Review Board/Independent Ethics Committee (IRB/IEC), and regulatory authorities according to applicable regulations prior to initiation of the study.

All potential serious breaches must be reported to the Sponsor or designee immediately. A potential serious breach is defined as a Quality Issue (eg, protocol deviation) that is likely to affect, to a significant degree, one or more of the following: (1) the rights, physical safety or mental integrity of one or more participants; (2) the scientific value of the clinical trial (eg, reliability and robustness of generated data). Items (1) or (2) can be associated with either GCP regulation(s) or trial protocol(s).

Personnel involved in conducting this study will be qualified by education, training, and experience to perform their respective tasks.

This study will not use the services of study personnel where sanctions have been invoked or where there has been scientific misconduct or fraud (eg, loss of medical licensure, debarment).

INSTITUTIONAL REVIEW BOARD/INDEPENDENT ETHICS COMMITTEE

Before study initiation, the investigator must have written and dated approval/favorable opinion from the IRB/IEC for the protocol, Investigator's Brochure, product labeling information, ICF, participant recruitment materials (eg, advertisements), and any other written information to be provided to participants.

The investigator, Sponsor, or designee should provide the IRB/IEC with reports, updates, and other information (eg, expedited safety reports, amendments, administrative letters) annually, or more frequently, in accordance with regulatory requirements or institution procedures.

Protocol Amendment No.: 02

Approved v 3.0 930159159 3.0

The investigator is responsible for providing oversight of the conduct of the study at the site and adherence to requirements of the following where applicable:

- ICH guidelines,
- United States Code of Federal Regulations, Title 21, Part 50 (21CFR50)
- European Union Directive 2001/20/EC; or
- European Regulation 536/2014 for clinical studies (if applicable),
- European Medical Device Regulation 2017/745 for clinical device research (if applicable),
- the IRB/IEC
- and all other applicable local regulations.

COMPLIANCE WITH THE PROTOCOL AND PROTOCOL REVISIONS

The investigator should not implement any deviation or change to the protocol without prior review and documented approval/favorable opinion of an amendment from the IRB/IEC (and, if applicable, also by the local Health Authority), except where necessary to eliminate an immediate hazard(s) to study participants.

If a deviation or change to a protocol is implemented to eliminate an immediate hazard(s) prior to obtaining relevant approval/favorable opinion(s), the deviation or change will be submitted as soon as possible to:

- IRB/IEC
- Regulatory authority(ies), if applicable by local regulations (per national requirements)

Documentation of approval/favorable opinion signed by the chairperson or designee of the IRB(s)/IEC(s) and, if applicable, also by the local Health Authority, must be sent to Bristol-Myers Squibb (BMS).

If an amendment substantially alters the study design or increases the potential risk to the participant: (1) the ICF must be revised and submitted to the IRB(s)/IEC(s) for review and approval/favorable opinion; (2) the revised form must be used to obtain consent from participants currently enrolled in the study if they are affected by the amendment; and (3) the new form must be used to obtain consent from new participants prior to enrollment.

FINANCIAL DISCLOSURE

Investigators and sub-investigators will provide the Sponsor with sufficient, accurate financial information, in accordance with regulations, to allow the Sponsor to submit complete and accurate financial certification or disclosure statements to the appropriate Health Authorities. Investigators are responsible for providing information on financial interests during the course of the study and for 1 year after completion of the study.

INFORMED CONSENT PROCESS

Investigators must ensure that participants are clearly and fully informed about the purpose, potential risks, and other critical issues regarding clinical studies in which they volunteer to participate.

The Sponsor or designee will provide the investigator with an appropriate sample ICF, which will include all elements required by the ICH GCP, and applicable regulatory requirements. The sample ICF will adhere to the ethical principles that have their origin in the Declaration of Helsinki.

The investigator or his/her representative must:

- Obtain IRB/IEC written approval/favorable opinion of the written ICF and any other information to be provided to the participant prior to the beginning of the study and after any revisions are completed for new information.
- Provide a copy of the ICF and written information about the study in the language in which the participant is proficient prior to clinical study participation. The language must be nontechnical and easily understood.
- Explain the nature of the study to the participant or his/her legally acceptable representative and answer all questions regarding the study.
- Inform participant that his/her participation is voluntary. Participant or his/her legally acceptable representative will be required to sign a statement of informed consent that meets the requirements of 21 CFR 50, local regulations, ICH guidelines, Health Insurance Portability and Accountability Act (HIPAA) requirements, where applicable, and the IRB/IEC or study center.
- Allow time necessary for participant or his/her legally acceptable representative to inquire about the details of the study.

Obtain an ICF signed and personally dated by participant or his/her legally acceptable representative and by the person who conducted the informed consent discussion.

- Include a statement in participant's medical record that written informed consent was obtained before participant was enrolled in the study and the date the written consent was obtained. The authorized person obtaining the informed consent must also sign the ICF.
- Re-consent participant to the most current version of the ICF(s) during his/her participation in the study, as applicable.

Revise the ICF whenever important new information becomes available that is relevant to the participant's consent. The investigator, or a person designated by the investigator, should fully inform the participant or his/her legally acceptable representative of all pertinent aspects of the study and of any new information relevant to the participant's willingness to continue participation in the study. This communication should be documented.

The confidentiality of records that could identify participants must be protected, respecting the privacy and confidentiality rules applicable to regulatory requirements, the participant's signed ICF, and, in the US, the participant's signed HIPAA Authorization.

The ICF must also include a statement that BMS and local and foreign regulatory authorities have direct access to participant records.

In situations where consent cannot be given by participants, their legally acceptable representatives (as per country regulation) are clearly and fully informed about the purpose, potential risks, and other critical issues regarding clinical studies in which the participant volunteers to participate.

If informed consent is initially given by a participant's legally acceptable representative or legal guardian and the participant subsequently becomes capable of making and communicating his or her informed consent during the study, consent must additionally be obtained from the participant.

Participant unable to give their written informed consent (eg, stroke or participants with severe dementia) may only be enrolled in the study with the consent of a legally acceptable representative. The participant must also be informed about the nature of the study to the extent compatible with his or her understanding, and should this participant become capable, he or she should personally sign and date the ICF as soon as possible. The explicit wish of a participant who is unable to give his or her written consent, but who is capable of forming an opinion and assessing information to refuse participation in, or to be withdrawn from, the clinical study at any time, should be considered by the investigator.

The rights, safety, and well-being of the study participants are the most important considerations and should prevail over interests of science and society.

BMS COMMITMENT TO DIVERSITY IN CLINICAL TRIALS

The mission of BMS is to transform patients' lives through science by discovering, developing, and delivering innovative medicines that help them prevail over serious diseases.

BMS is committed to doing its part to ensure that patients have a fair and just opportunity to achieve optimal health outcomes.

BMS is working to improve the recruitment of a diverse participant population with the goal that the clinical trial becomes more reflective of the real-world population and the people impacted by the diseases studied.

DATA PROTECTION, DATA PRIVACY, AND DATA SECURITY

BMS collects and processes personal data of study participants, patients, health care providers, and researchers for biopharmaceutical research and development to advance innovative, high-quality medicines that address the medical needs of patients. BMS ensures the privacy, protection, and confidentiality of such personal data to comply with applicable laws. To achieve these goals, BMS has internal policies that indicate measures and controls for processing personal data. BMS adheres to these standards to ensure that collection and processing of personal data are limited and proportionate to the purpose for which BMS collects such personal data. This purpose is clearly and unambiguously notified to the individual at the time of collection of personal data. In the true

spirit of science, BMS is dedicated to sharing clinical trial information and data with participants, medical/research communities, the media, policy makers, and the general public. This is done in a manner that safeguards participant privacy and informed consent while respecting the integrity of national regulatory systems. Clinical trial data, health-related research, and pharmacovigilance activities on key-coded health data transferred by BMS across national borders is done in compliance with the relevant data protection laws in the country and GCP requirements.

BMS protects Personal Information with adequate and appropriate security controls as indicated under the data protection laws. To align with the recommended security standards, BMS has adopted internal security standards and policies to protect personal data at every stage of its processing.

To supplement these standards, BMS enters into Clinical Trial Agreements (CTAgs) with confidentiality obligations to ensure proper handling and protection of personal data by third parties accessing and handling personal data.

BMS takes unauthorized access and disclosure of Personal Information very seriously. BMS has adopted the security standards that include National Institute of Standards and Technology Cybersecurity Framework for studies in the US. BMS aligns with these standards to continuously assess and improve its ability to protect, detect, and respond to cyber attacks and other unauthorized attempts to access personal data. These standards also aid in mitigating possible adverse effects. Furthermore, BMS Information Technology has defined 6 principles to protect our digital resources and information:

- 1) Responsibilities of IT Personnel
- 2) Securing the BMS Digital Infrastructure
- 3) Identity and Access Management
- 4) External Partner Connections
- 5) Cyber Threat Detection and Response
- 6) Internal Cyber Incident Investigation

SOURCE DOCUMENTS

Source documents provide evidence for the existence of the participant and substantiate the integrity of the data collected. Source documents are filed at the investigator's site.

Data reported on the CRF or entered in the electronic CRF (eCRF) that are transcribed from source documents must be consistent with the source documents or the discrepancies must be explained.

- The investigator may need to request previous medical records or transfer records, depending on the study. Also, current medical records must be available.
- Definitions of what constitutes source data can be found in systems that may include, but are not limited to, electronic medical/health records (EMRs/EHRs), adverse event tracking/reporting, protocol required assessments, and/or drug accountability records).

The investigator is responsible for ensuring that the source data are accurate, legible, contemporaneous, original, and attributable, whether the data are handwritten on paper or entered electronically. If source data are created (first entered), modified, maintained, archived, retrieved, or transmitted electronically via computerized systems (and/or any other kind of electronic devices) as part of regulated clinical trial activities, such systems must be compliant with all applicable laws and regulations governing use of electronic records and/or electronic signatures. Such systems may include, but are not limited to, electronic medical records/electronic health records, adverse event (AE) tracking/reporting, protocol-required assessments, and/or drug accountability records.

When paper records from such systems are used in place of an electronic format to perform regulated activities, such paper records should be certified copies. A certified copy consists of a copy of original information that has been verified, as indicated by a dated signature, as an exact copy having all of the same attributes and information as the original.

STUDY INTERVENTION RECORDS

Records for study intervention (whether supplied by BMS, its vendors, or the site) must substantiate study intervention integrity and traceability from receipt, preparation, administration, and through destruction or return. Records must be made available for review at the request of BMS/designee or a Health Authority.

If	Then
Supplied by BMS (or its vendors):	Records or logs must comply with applicable regulations and guidelines and should include: • amount received and placed in storage area • amount currently in storage area
	 label identification number or batch number amount dispensed to and returned by each participant, including unique participant identifiers
	amount transferred to another area/site for dispensing or storage
	• nonstudy disposition (eg, lost, wasted)
	amount destroyed at study site, if applicable
	amount returned to BMS
	• retain samples for bioavailability/bioequivalence/biocomparability, if applicable
	dates and initials of person responsible for Investigational Product dispensing/accountability, as per the Delegation of Authority Form
Sourced by site and not supplied by BMS or its vendors (examples include IP sourced from the sites stock or commercial supply or a specialty pharmacy)	The investigator or designee accepts responsibility for documenting traceability and study treatment integrity in accordance with requirements applicable under law and the standard operating procedures/standards of the sourcing pharmacy

BMS or its designee will provide forms to facilitate inventory control if the investigational site does not have an established system that meets these requirements.

CASE REPORT FORMS

An investigator is required to prepare and maintain adequate and accurate case histories designed to record all observations and other data pertinent to the investigation on each individual treated or entered as a control in the investigation. Data that are derived from source documents and reported on the CRF must be consistent with the source documents, or the discrepancies must be explained. Additional clinical information may be collected and analyzed in an effort to enhance understanding of product safety. CRFs may be requested for AEs and/or laboratory abnormalities that are reported or identified during the course of the study.

For sites using the Sponsor or designee electronic data capture (EDC) tool, eCRFs will be prepared for all data collection fields except for fields specific to SAEs and pregnancy, which will be reported on the electronic SAE form and Pregnancy Surveillance Form, respectively. If the

Protocol Amendment No.: 02

electronic SAE form is not available, a paper SAE form can be used. Spaces may be left blank only in those circumstances permitted by study-specific CRF completion guidelines provided by the Sponsor or designee.

The confidentiality of records that could identify participants must be protected, respecting the privacy and confidentiality rules in accordance with the applicable regulatory requirement(s).

The investigator will maintain a signature sheet to document signatures and initials of all persons authorized to make entries and/or corrections on CRFs.

